10.6 Response Review

Central radiology review is not planned, as most patients will proceed to chemoradiation and surgery after restaging.

11 ADVERSE EVENT REPORTING REQUIREMENTS

11.1 Definitions

11.1.1 Adverse Event (AE)

An adverse event (AE) is any undesirable sign, symptom or medical condition or experience that develops or worsens in severity after starting the first dose of study treatment or any procedure specified in the protocol, even if the event is not considered to be related to the study.

Abnormal laboratory values or diagnostic test results constitute adverse events only if they induce clinical signs or symptoms or require treatment or further diagnostic tests.

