6 EXPECTED TOXICITIES AND DOSING DELAYS/MODIFICATIONS

Dose delays and modifications will be made using the following recommendations. Toxicity assessments will be done using the CTEP Active Version of the NCI Common Terminology Criteria for Adverse Events (CTCAE) which is identified and located on the CTEP website at: http://ctep.cancer.gov/protocolDevelopment/electronic_applications/ctc.htm.

If possible, symptoms should be managed symptomatically. In the case of toxicity, appropriate medical treatment should be used (including anti-emetics, anti-diarrheals, etc.).

All adverse events experienced by participants will be collected from the time of the first dose of study treatment, through the study and until the final study visit. Participants continuing to experience toxicity at the off study visit may be contacted for additional assessments until the toxicity has resolved or is deemed irreversible.

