6.1.1 FOLFIRINOX Therapy

6.1.1.1 Anticipated Hematologic adverse events

Below is the table of adverse events associated with the FOLFIRINOX regimen in the Prodiges-4/ACCORD trial in patients with advanced pancreatic adenocarcinoma.

AE, % per patient	Folfirinox	
	N=171 (from NEJM 2011)	
	All	Grade 3/4
Neutropenia	79.9	45.7
Febrile Neutropenia	5.4	
Anemia	90.4	7.8
Thrombocytopenia	75.2	9.1

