6.2.1.1 Hematologic toxicities

The following dose modifications are based on toxicity demonstrated during a mid-cycle visit and/or at the time of laboratory assessment for planned administration of the next cycle of therapy (for example on the planned day of administration of Cycle 2 Day 1 after completing the 14-day period constituting Cycle 1.) As the Grade 2-4 neutropenia rate in the PRODIGE-ACCORD trial was 79.9%, in this trial prophylactic GM-CSF (Neulasta) will be administered 24-48 hours after discontinuation of continuous infusion 5-FU.

Dose Reduction Table for Hematologic Toxicity

(Note: DR = Dose Reduction)

Hematologic Toxicity on the Day of Treatment (D1)	Action	Oxaliplatin	Irinotecan	5-FU Bolus (Leucovorin follows protocol for 5FU bolus)	5-FU Continuous Infusion
Neutropenia G2 (ANC 1500-1000) – all patients should have Neulasta support per institutional guidelines	HOLD ALL THERAPY	Hold until ANC \geq 1500, resume without dose reduction	Hold until ANC \geq 1500, resume without dose reduction	Hold until ANC \geq 1500, resume without dose reduction	Hold until ANC \geq 1500, resume without dose reduction
Neutropenia G3-4, Febrile neutropenia (ANC 1000-500, <500)	HOLD ALL THERAPY, Supportive care and antibiotics per institutional guidelines	Hold until ANC \geq 1500, resume @ permanent DL-1 level once resolved	Hold until ANC \geq 1500, resume @ permanent DL-1 level once resolved	Hold until ANC \geq 1500, resume @ permanent DL-1 level once resolved	Hold until ANC \geq 1500, resume @ permanent DL-1 level once resolved
Thrombocytopenia G1 (LLN – 75K)	Treat with DR Oxaliplatin	Treat at permanent DL -1	No reduction	No reduction	No reduction

Thrombocytopenia G2 (75K – 50K)	HOLD ALL THERAPY	Hold until resolved to >100K, resume at permanent DL-1	Hold until resolved to >100K, no reduction	Hold until resolved to >100K, No reduction	Hold until resolved to >100K, No reduction
Thrombocytopenia G3-4 (50K – 25K, <25K)	HOLD ALL THERAPY	Hold until resolved to >100K. Resume @ permanent DL-1 if resolved in 1 wk, permanent DL -2 if >1 wk to resolve	Hold until resolved to >100K. Resume @ permanent DL-1.	Hold until resolved to >100K	Hold until resolved to >100K

6.2.1.2 Gastrointestinal toxicities:

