11.2 Procedures for AE and SAE Recording and Reporting

Reporting Participating investigators will assess the occurrence of AEs and SAEs at all participant evaluation time points during the study.

All AEs and SAEs whether reported by the participant, discovered during questioning, directly observed, or detected by physical examination, laboratory test or other means, will be recorded in the participant's medical record and on the appropriate study-specific case report forms.

The descriptions and grading scales found in the CTEP Active Version of the NCI Common Terminology Criteria for Adverse Events (CTCAE) will be utilized for AE reporting. The CTEP Active Version of the CTCAE is identified and located on the CTEP website at:

http://ctep.cancer.gov/protocolDevelopment/electronic_applications/ctc.htm.

All appropriate treatment areas should have access to a copy of the CTEP Active Version of CTCAE.

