11.4.2 Non-Serious Adverse Event Reporting

Non-serious adverse events will be reported to the DF/HCC Overall Principal Investigator on the toxicity Case Report Forms.

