14.4 Analysis of Secondary Endpoints

Progression-free survival: All patients who start the protocol therapy will be analyzed based on the definition in Section 10.1.3. The Kaplan-Meier method will be used to estimate progression-free survival with 90% confidence intervals constructed by Greenwood's formula.

Overall survival: Overall survival will be defined as the duration between the dates of protocol enrollment and death. The survival time of patients who are not known to have died will be censored at the date they were last known to be alive.

Toxicity: All patients who begin protocol treatment will be included in the toxicity profile. Toxicity summaries will include the frequency and proportion of patients experiencing each type of toxicity, as well as summaries by toxicity category and grade.

Surgical morbidity: Analysis will be based on the patients who undergo pancreaticoduodenectomy or distal pancreatectomy. The surgical morbidity rate will be calculated as the proportion of patients who experience peri- and post-operative complications within 30 days of surgery. A 90% confidence interval will be obtained using the exact binomial distribution.

30-day post-operative mortality rate: Analysis will be based on the patients who undergo pancreaticoduodenectomy or distal pancreatectomy. The 30-day post-operative mortality rate will be calculated as the number of patients who die within 30 days of surgery. A 90% confidence interval will be obtained using the exact binomial distribution.

Pathologic downstaging: Analysis will be based on the patients who undergo pancreaticoduodenectomy or distal pancreatectomy. The pathologic downstaging rate will be calculated as the proportion of patients with the primary tumor and nodes downstaged based on final pathology of the surgical specimen.

Local control rate: Local control will be defined as the time from protocol enrollment to the first objective documentation of local failure. Patients who have not experienced a local failure will be censored at the last date they were known to have local control. Kaplan-Meier methodology will be used to estimate the local control rate.

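### Section 14.4 does not say whether laboratory toxicity follows the restricted adverse event definition in 11.1.1 or the bare grades used in section 6, so asymptomatic low-grade events may be under-recorded

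*Combined protocol and SAP*

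**What the plan says.** Toxicity of the regimen is secondary objective 1.3.3. The combined protocol and SAP handles laboratory findings in two ways.

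**Restricted rule.** Section 11.1.1 says: "Abnormal laboratory values or diagnostic test results constitute adverse events only if they induce clinical signs or symptoms or require treatment". Read to its end, the sentence admits a laboratory abnormality as an adverse event "only if they induce clinical signs or symptoms or require treatment or further diagnostic tests". Section 11.4.2 then says: "Non-serious adverse events will be reported to the DF/HCC Overall Principal Investigator on the toxicity Case Report Forms". Section 12.1.2 lists one combined toxicity and adverse event form, and a separate Lab Form due after each protocol-defined laboratory assessment.

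**Grade-based rule.** Section 6 says: "Toxicity assessments will be done using the CTEP Active Version of the NCI Common Terminology Criteria for Adverse Events (CTCAE"). Section 6.1.1.1 introduces its hematologic table with "Below is the table of adverse events associated with the FOLFIRINOX regimen in the Prodiges-4/ACCORD trial" and gives neutropenia, anemia and thrombocytopenia for all grades and for grade 3/4. Section 6.1.1.2 does the same for ALT. Section 6.2.1.1 opens with "The following dose modifications are based on toxicity demonstrated during a mid-cycle visit and/or at the time of laboratory assessment", and its table acts on neutrophil and platelet counts with no symptom requirement.

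**Analysis.** Section 14.4 says: "Toxicity summaries will include the frequency and proportion of patients experiencing each type of toxicity, as well as summaries by toxicity category and grade". It names no data source and does not mention 11.1.1.

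**The concern.** Both rules are operative, and they classify some of the same values differently. The adverse event definition can decide what reaches the toxicity form, and that form is the natural source for the 14.4 summaries. If sites apply 11.1.1 literally, a graded laboratory toxicity in the sense of section 6 may never be entered. Sites may also differ on whether a dose reduction, a hold or a repeat count is a treatment or an additional test. The same count could then be a graded toxicity in one patient and absent in another.

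The error runs one way: events can be left out but not added, so the laboratory part of the safety profile can only look better than it was. A reader would naturally look at the reported rates beside the all-grade rates in 6.1.1 and could be misled.

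**Working it through.** The plan states no figure on this point, so there is none to reproduce. The check has two parts.

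**1. Which values can fail every route in 11.1.1?**

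- *Grade 1 thrombocytopenia (lower limit of normal to 75K).* Section 6.2.1.1 gives oxaliplatin at a permanently lower dose level and does not hold therapy. No repeat count is implied. The scheduled blood count in section 9 is not clearly an extra test, and a dose reduction is not clearly a treatment of the finding. A value that permanently changes dosing can therefore go unrecorded.
- *Asymptomatic grade 1-2 anemia and ALT rises.* The 6.2.1.1 table has no anemia row and the 6.2.1.2 table has no ALT row, so no protocol action during treatment would bring them in.
- *Grade 2-4 neutropenia and grade 2-4 thrombocytopenia.* All therapy is held until counts recover. Recovery cannot be shown without repeat counts, and the grade 3-4 neutropenia row also calls for supportive care and antibiotics. Most of these would probably qualify, although the text does not say that a hold or a repeat count suffices.

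**2. How much could be omitted?**

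Inputs are the reference rates in 6.1.1.1 and 6.1.1.2 (percent of patients) and the accrual goal of 50 in 14.2. Let A be the all-grade rate, G the grade 3/4 rate and f the fraction of grade 1-2 events that still meet 11.1.1. Assume that all grade 3/4 events qualify. Then:

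- grade 1-2 rate = A − G
- recorded all-grade rate = G + f(A − G)
- largest omitted share (f = 0) = (A − G)/A

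| Event | A | G | A − G | Recorded at f = 0 / 0.5 / 1 | Largest omitted share | Grade 1-2 patients per 50 |
|---|---|---|---|---|---|---|
| Neutropenia | 79.9 | 45.7 | 34.2 | 45.7 / 62.8 / 79.9 | 34.2/79.9 = 43% | 17.1 |
| Thrombocytopenia | 75.2 | 9.1 | 66.1 | 9.1 / 42.15 / 75.2 | 66.1/75.2 = 88% | 33.05 |
| ALT | 64.8 | 7.3 | 57.5 | 7.3 / 36.05 / 64.8 | 57.5/64.8 = 89% | 28.75 |
| Anemia | 90.4 | 7.8 | 82.6 | 7.8 / 49.1 / 90.4 | 82.6/90.4 = 91% | 41.3 |

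The smallest omitted share is 0 in every row (f = 1). The documents do not give f, so the range is the result. The upper ends for neutropenia and thrombocytopenia are generous, because they treat grade 2 events as lost although part 1 suggests that many would qualify. The tables do not separate grade 1 from grade 2, so the bound cannot be tightened.

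The neutropenia row takes 79.9% as all grades, as 6.1.1.1 labels it. Section 6.2.1.1 calls the same figure grade 2-4, and section 5.3 appears to attach it to grade 3-4. These passages should be reconciled.

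**The case against.** A reader might infer that the definition drops asymptomatic laboratory abnormalities altogether, and that most cytopenias, severe ones included, will be lost. Scaling to 50 patients seems to support this: grade 3/4 neutropenia is 50 × 0.457 = 22.9 patients, but febrile neutropenia only 50 × 0.054 = 2.7. The documents do not support that reading. An asymptomatic value still counts if it needs treatment or more tests, and fever is a poor proxy for meeting the definition. Section 2.2.4 reports that 42.5% of FOLFIRINOX patients in the same reference trial required G-CSF, or 50 × 0.425 = 21.3 of 50, close to the 22.9, although the overlap of patients is not given. Likewise, an asymptomatic grade 3 platelet count leads to a hold, and so to repeat counts.

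The other objections are fair:

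- Section 14.4 speaks of toxicity, not of 11.1.1 events. Section 11.2 covers adverse events "directly observed, or detected by physical examination, laboratory test or other means". No sentence says that the toxicity form holds only 11.1.1 events.
- The Lab Form keeps the scheduled values. Section 9 has blood counts and chemistries on day 1 of each cycle and on days 1, 8 and 15 of chemoradiation, so those data are not lost.
- No formal comparison with the reference rates is planned. The metastatic reference population and the prophylactic growth factor in 6.2.1.1 would limit one in any case.

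These points make omission a risk and not a certainty, and they make the remedy cheap. They do not settle which rule applies: 11.2 still relies on the 11.1.1 definition of an adverse event, and no section says that grades will be derived from the Lab Form.

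**Conclusion.** The concern holds as a conflict between stated rules that 14.4 leaves unresolved. Asymptomatic low-grade laboratory toxicity may be under-recorded in a rater-dependent way, chiefly anemia, ALT rises and grade 1 thrombocytopenia. A recorded all-grade thrombocytopenia rate anywhere from 9.1% to 75.2% could be consistent with the text.

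This size rests on two assumptions: that the protocol's reference rates apply to these patients, and that all grade 3/4 events qualify. Prophylactic growth factor would probably lower the neutropenia rates. The documents do not show that most events will be omitted, and for neutropenia the share cannot exceed 43% under these assumptions.

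The primary endpoint is unaffected, since R0 resection is read from final pathology. This is a descriptive secondary endpoint, and the change is worth making because it is cheap and removes a one-directional error.

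**What to change.** - In 14.4, state that laboratory toxicity (neutrophils, platelets, hemoglobin, AST, ALT, bilirubin, alkaline phosphatase, creatinine) is summarised as the worst CTCAE grade per patient, derived from all collected Lab Form values whether or not symptoms or treatment occurred.
- In 11.1.1, limit the laboratory filter to SAE and expedited reporting.
- In 12.1.2, ask that unscheduled values leading to a dose modification under 6.2.1.1 also go on the Lab Form, because its timeline now covers only protocol-defined assessments.

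No treatment rule changes. The cost is about one sentence in each place, programmed grading of data mostly collected already, entry of some unscheduled values, and reported laboratory toxicity rates that will look less favourable.

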11.1.2 Serious adverse event (SAE)

A serious adverse event (SAE) is any adverse event, occurring at any dose and regardless of causality that:

- Results in death
- Is life-threatening. Life-threatening means that the person was at immediate risk of death from the reaction as it occurred, i.e., it does not include a reaction which hypothetically might have caused death had it occurred in a more severe form.
- Requires or prolongs inpatient hospitalization (i.e., the event required at least a 24-hour hospitalization or prolonged a hospitalization beyond the expected length of stay). Hospitalization admissions and/or surgical operations scheduled to occur during the study period, but planned prior to study entry are not considered SAEs if the illness or disease existed before the person was enrolled in the trial, provided that it did not deteriorate in an unexpected manner during the trial (e.g., surgery performed earlier than planned).
- Results in persistent or significant disability/incapacity. Disability is defined as a substantial disruption of a person's ability to conduct normal life functions.
- Is a congenital anomaly or birth defect; or
- Is an important medical event when, based upon appropriate medical judgment, it may jeopardize the participant and require medical or surgical intervention to prevent one of the outcomes listed above. Examples of such medical events include allergic bronchospasm requiring intensive treatment in an emergency room or at home; blood dyscrasias or convulsions that do not result in inpatient hospitalization, or the development of drug dependency or drug abuse.

Events **not** considered to be serious adverse events are hospitalizations for:

- routine treatment or monitoring of the studied indication, not associated with any deterioration in condition, or for elective procedures

- elective or pre-planned treatment for a pre-existing condition that did not worsen
- emergency outpatient treatment for an event not fulfilling the serious criteria outlined above and not resulting in inpatient admission
- respite care
- grade 4 lipase and lymphocytes

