5.2.6 Radiation Therapy

5.2.6.1 Simulation and Planning

Tumor volume will be defined on the basis of CT and MRI imaging findings and operative notes and findings. The primary tumor and any clinically enlarged lymph nodes will be treated with a margin of 2 cm to include peripancreatic nodes. The porta hepatis, celiac axis, superior mesenteric artery (SMA) root, and the pancreaticoduodenal nodes will also be treated.

Total dose will be prescribed to the 95 to 100% isodose line based on coverage and will be 25 CGE protons in 5 fractions (5 Gy/day) or 30 Gy photons in 10 fractions (3 Gy/day) with multifield techniques. A dose painted boost to involved vasculature is permitted to a total dose of 30 Gy. Radiation treatment assignment will be based on resource availability at the time of radiation planning.

Patients will be simulated supine. Intravenous and oral contrast will be administered per standard department protocol. 4-D planning CT will be obtained for treatment planning to ascertain the extent of tumor motion.

The Gross Tumor Volume (GTV) is defined as the gross primary tumor and any lymph nodes enlarged over 1 cm during simulation using contrast given during CT or MRI. The clinical target volume (CTV) will also include the following at-risk nodal basins: porta hepatis, celiac axis, superior mesenteric artery, and pancreaticoduodenal nodes as defined by the inner-third of the duodenum. Planning target volume (PTV): PTV will be customized based on 4D CT scan. Generally 0.5 cm expansion will be used, except for superiorly/inferiorly 0.7 cm will be used.

Computerized dosimetry is required if more than two fields are used. All fields must be simulated using a machine that duplicates the geometry of the actual treatment machine. Patient contours and isodose plots are required. Isodose plots must account for the effect of all treated fields, including any blocking used.

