11.4 Reporting to the Study Sponsor

11.4.1 Serious Adverse Event Reporting

All serious adverse events that occur after the initial dose of study treatment, during treatment, or within 30 days of the last dose of treatment must be reported to the DF/HCC Overall Principal Investigator on the local institutional SAE form. This includes events meeting the criteria outlined in Section 11.1.2, as well as the following:

- Grade 2 (moderate) and Grade 3 (severe) events that are unexpected and at least possibly related/associated with the intervention.
- All Grade 4 (life-threatening or disabling) events that are unexpected AND not specifically listed in the protocol as not requiring reporting.
- All Grade 5 (fatal) events while the participant is enrolled and actively participating in the trial OR when the event occurs within 30 days of the last study intervention.

Note: If the participant is in long term follow up, report the death at the time of continuing review.

Participating investigators must report each serious adverse event to the DF/HCC Overall Principal Investigator within 24 hours of learning of the occurrence. In the event that the participating investigator does not become aware of the serious adverse event immediately (e.g., participant sought treatment elsewhere), the participating investigator is to report the event within 24 hours after learning of it and document the time of his or

her first awareness of the adverse event. Report serious adverse events by telephone, email or facsimile to:

[name].

Within the following 48 hours, the participating investigator must provide follow-up information on the serious adverse event. Follow-up information should describe whether the event has resolved or continues, if and how the event was treated, and whether the participant will continue or discontinue study participation.

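### The serious adverse event definition lists grade 4 lipase and lymphocytes among exempt hospitalizations, contradicting its own hospitalization criterion, so an admission recorded under either term may miss the 24-hour report

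*Combined protocol and SAP*

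**What the plan says.** Section 11.1.2 sets out when an adverse event is serious, whatever its cause. One criterion is "Requires or prolongs inpatient hospitalization". The section then gives a list of exceptions, introduced as events not "considered to be serious adverse events are hospitalizations for" certain reasons. The last entry is "grade 4 lipase and lymphocytes". It is not limited to asymptomatic or isolated values, or to patients who were not admitted.

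Section 11.4.1 takes the scope of 24-hour reporting from that definition and adds to it: "This includes events meeting the criteria outlined in Section 11.1.2, as well as the following". One addition is "All Grade 4 (life-threatening or disabling) events that are unexpected AND not specifically listed in the protocol as not requiring reporting".

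Section 11.1.1 decides when a laboratory result is an adverse event at all. Abnormal values "constitute adverse events only if they induce clinical signs or symptoms or require treatment or further diagnostic tests".

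**The concern.** The same section makes an admission serious and then, for two named laboratory toxicities, makes it not serious. A site that follows the exception literally would not send the 24-hour report or the further information due within the next 48 hours.

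This matters for lipase in this trial because the pancreas is irradiated. Section 5.2.6.1 states: "The primary tumor and any clinically enlarged lymph nodes will be treated with a margin of 2 cm to include peripancreatic nodes". Lipase is not among the laboratory tests in Section 5.1 or the Section 9 calendar. A grade 4 value would therefore mostly come from a test ordered for a clinical reason, in a patient more likely to have symptoms or be admitted.

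That argument does not carry over to lymphocytes. The blood count with differential is scheduled on day 1 of each FOLFIRINOX cycle and on days 1, 8 and 15 of chemoradiation, so low lymphocyte counts will surface routinely in patients without symptoms.

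**Working it through.** No arithmetic applies. The check is to run the possible situations through Sections 11.1.1, 11.1.2 and 11.4.1 and see where the exception changes the answer.

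| Situation | Adverse event (11.1.1)? | Serious (11.1.2)? | Added grade 4 route (11.4.1) |
|---|---|---|---|
| A. Grade 4 value; no symptoms, treatment or further tests | No | No | Not reached |
| B. Grade 4 value, no symptoms, prompts a further test; no admission | Yes | Not by hospitalization | Applies if unexpected, unless the 11.1.2 item counts as a listing |
| C. Admission recorded as grade 4 lipase or lymphocyte toxicity | Yes | Criterion says yes, exception says no | As in B |
| D. The same admission recorded as a diagnosis such as pancreatitis | Yes | Yes; the diagnosis is not on the list | Not needed |
| E. Event that is fatal, life-threatening, disabling or an important medical event | Yes | Yes, under those criteria | Not needed |

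1. In A the exception has nothing to do, because Section 11.1.1 has already excluded the value.
2. In B there is no admission to exempt. If the drafters wanted to keep such values out of grade 4 reporting, the place to say so is Section 11.4.1.
3. C is therefore the only case that fits the list in which the item stands, and there it contradicts the hospitalization criterion.
4. The added grade 4 route does not clearly rescue C, for two reasons. First, it leaves out events the protocol specifically lists as not requiring reporting. The Section 11.1.2 item is the only place that names specific grade 4 findings as exempt, but it speaks of seriousness rather than reporting, so whether it is such a listing is open. Second, the route needs the event to be unexpected. Lipase does not appear in the Section 6.1 lists, but Section 11.1.3.1 also counts package inserts and the consent form, which cannot be checked here.
5. C and D can describe the same patient. Whether the admission is serious then depends on the term entered on the form.

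What remains in place for C if it is classed as non-serious:

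- Section 11.4.2 sends it to the overall principal investigator on the toxicity form. Section 12.1.2 has that form submitted every two weeks during FOLFIRINOX and weekly during chemoradiation.
- Section 11.7 requires follow-up of serious and non-serious events alike until they resolve, are stable or are judged irreversible.
- Section 12.2 gives the monitoring committee toxicity data, which may include reported unexpected events of grade 2 or higher.
- Section 14.4 includes all treated patients in the toxicity summaries and tabulates hospitalizations and intensive care stays.

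During preoperative treatment, the practical difference is a toxicity form on a one- or two-week cycle in place of a report within 24 hours.

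**The case against.** The strongest reply is that the list is loose. Another entry concerns emergency outpatient treatment that did not lead to admission, which is not a hospitalization either. On that view the lead-in does not govern every item, and the lipase and lymphocyte entry was meant for isolated laboratory values. This is plausible as intent. It does not settle the matter, because the text states no such limit and Section 11.1.1 already removes most isolated values.

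The reply is right about the consequences. A reader might infer that every admission with a high lipase escapes serious event reporting, or that such cases drop out of safety review. The documents support neither. The item names a laboratory grade, so an admission recorded as a diagnosis is still serious, the other seriousness criteria are untouched, and grade 5 events stay reportable. Non-serious events still reach the investigator, the monitoring committee's toxicity review and the toxicity tables.

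A reader might also infer that Section 11.4.1 definitely exempts these events. That goes too far as well: Section 11.1.2 never says they need not be reported, and a site could defend reporting an unexpected grade 4 lipase.

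**Conclusion.** The point holds in a narrow form: wrong as written, low severity. Section 11.1.2 contradicts itself for an admission recorded as grade 4 lipase or lymphocyte toxicity, and Section 11.4.1 does not clearly resolve it. What may be lost is the expedited report, not oversight as a whole. Classification also becomes dependent on the site's choice of term.

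The size cannot be given as a number, because the documents contain no rate for either event. Few lipase cases seem likely, since the test is not scheduled, but those found would tend to be symptomatic. The primary endpoint, sample size and efficacy analyses are unaffected. The conclusion assumes that sites apply the list as worded.

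**What to change.** Reconcile Sections 11.1.2 and 11.4.1. Remove the lipase and lymphocyte item from the hospitalization exceptions. If an exemption is wanted, state it in Section 11.4.1 as a listed exception to grade 4 reporting, limited to asymptomatic grade 4 lipase or lymphocyte values without hospitalization. Any admission then remains a serious adverse event under Section 11.1.2, whatever term the site records.

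The cost is moving and limiting one line, and possibly a few more serious adverse event reports. Treatment, endpoints and sample size do not change.
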